###### 3.3.1.1.2. Negative predictive value of the Whooley questions

Overall, we will calculate the number of pregnant women who answered *No* to both Whooley questions AND who scored 9 points or lower on the EPDS, as a proportion of the total number of pregnant women who answered *No* to both Whooley questions regardless of their EPDS scores.

###### 3.3.1.1.3. False omission rate of the Whooley questions

Overall, we will calculate the number of pregnant women who answered *No* to both Whooley questions AND who scored 10 points or higher on the EPDS, as a proportion of the total number of pregnant women who answered *No* to both Whooley questions regardless of their EPDS scores.

### 3.3.1.1.4. Mean overall scores on the EPDS

The score of each participant on the EPDS will be calculated automatically after survey completion. We will then compute the mean overall score on the EPDS for each experimental group.

### 3.3.1.1.5. Breakoff rates

For each experimental group, we will report the proportion of participants who interrupt the survey completion process before reaching the end of the survey questionnaires (i.e., breakoff rates). In such eventualities, we will document the reason for breakoff.

### 3.3.1.1.6. Time needed to complete survey questionnaires

This will be the time elapsed (in seconds) between the participants starting to read the basic instructions on how to complete the survey questionnaires and the participant completing the EPDS. These actions will be indicated by participants pressing the *Start* button on the device screen and when a message acknowledging that they have completed the survey questionnaires is displayed on the device screen. This component will be broken down further into the individual survey questionnaires that participants will be required to complete (i.e., personal demographic information, Whooley questions, and EPDS). In addition, we will account for the time that participants spend experiencing problems, distractions or making requests for help or clarification.

### 3.3.1.1.7. Proportion of complete EPDS records

A complete EPDS record will be defined as one in which no question was left unanswered. For each experimental group, we will compute the proportion of complete EPDS records.

Leaving unanswered questions in the *App Screening – Scrolling* and in the *App Screening – Paging* groups will not be possible due to the implementation of validation procedures. Therefore, data completeness will be indicated by the breakoff rates.

### 3.3.1.1.8. Proportion of participants requesting help

We will document the requests for help made by each participant, as well as the nature of the request. We will categorise participants into 3 groups: (i) one request for help; (ii) between 2 and 4 requests for help; and (iii) 5 or more requests for help. Subsequently, for each experimental group, we will compute the proportion of participants falling within each category.

### 3.3.1.1.9. Proportion of each type of request for help

We will document the requests for help made by each participant. We will conduct a content analysis of these requests in order to categorise them according to their nature. For each experimental group, we will compute the proportion of participants making each type of request.

## 3.3.1.2. App through a BYOD approach

### 3.3.1.2.1. Response rates

The proportion of potential participants who agree to take part in this study out of the total number of potential participants who are approached about participation in this study.

### 3.3.1.2.2. Drop-out rates

The proportion of participants who stop completing the retrospective or the retrospective plus momentary assessments before the end of the study (i.e., before 6 months). For those participants taking part in the app through a BYOD approach, we will consider they have dropped out if they miss 2 consecutive assessments. In this case, a notification on their phones will ask them to complete a question about the reason for not completing the assessments.

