### 2.2.2. Secondary Objectives

- To assess differences in drop-out rates between the participants allocated to the retrospective assessment strategy (i.e., EPDS), and those allocated to the retrospective plus momentary assessment strategy (i.e., EPDS complemented with the EMA of mood, sleep, energy, enjoyment and worry).
- To assess differences in participants' adherence to sampling protocols between a retrospective assessment strategy (i.e., EPDS), and a retrospective plus momentary assessment strategy (i.e., EPDS complemented with the EMA of mood, sleep, energy, enjoyment and worry). We will achieve this by comparing the proportion of participants in each group that complete 100% of the expected assessments.
- To assess differences in usage patterns of the app between a retrospective assessment strategy and a retrospective plus momentary assessment strategy, including additional voluntary self-reporting, time spent using the app, number of interactions with other sections of the app, time to complete the self-assessments, and other ancillary usage data
- To assess differences in participants' acceptance of the app between a retrospective assessment strategy and a retrospective plus momentary assessment strategy through a post-study self-administered questionnaire

- To assess differences in timeliness of data collection between a retrospective assessment strategy and a retrospective plus momentary assessment strategy. We will achieve this by comparing the proportion of participants completing their assessments in response to a prompt displayed on their mobile devices between the two groups
- To assess differences in data completeness between a retrospective assessment strategy and a retrospective plus momentary assessment strategy. We will achieve this by comparing the proportion of complete records between the two groups
- To evaluate the impact of a momentary assessment technique of the EPDS scores by comparing the EPDS scores obtained at the start of the sampling period and the EPDS scores obtained at the end of this period. This will be assessed in the *retrospective plus momentary assessment* condition only
- To assess if feedback provided by a healthcare practitioner influences participants' and clinicians' engagement, acceptance and perceived usefulness of an app used for the remote and longitudinal monitoring of mood symptoms throughout pregnancy

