## 3. Methods

### 3.1. Study Design

We will use a parallel, randomised control trial (RCT) study design. For the study assessing the use of tablet computers in antenatal clinics, participants will be randomly assigned to complete (i) an app version of the Whooley questions and the EPDS in which the questionnaires are presented using a scrolling layout (i.e., App screening – Scrolling), or (ii) an app version of the Whooley questions and the EPDS in which the questionnaires are presented using a paging layout (i.e., App screening – Paging).

Participants will also be asked if they wish to take part in the study evaluating an app through a BYOD approach. Those consenting to take part in this study will be randomly assigned to (i) complete the EPDS once a month for 6 months (i.e., retrospective assessment), or to (ii) complete the EPDS, plus 4 days of EMA of mood, sleep, worry, enjoyment and energy, plus EPDS once a month for 6 months (i.e., retrospective plus momentary assessment).

In selected sites, we will recruit an additional 30 participants into the app through a BYOD approach study. Participants recruited from these sites will receive feedback on their data from designated members of the clinical team.

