### 3.3.1.2.4. Timeliness of data collection

Each pre-specified assessment will be preceded by a prompt. Timeliness of data collection will be defined as the proportion of participants who complete the pre-specified assessments immediately after receiving this prompt.

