### 3.5.2.2.1. Retrospective assessment

Participants in this condition will be asked to complete the EPDS once a month for 6 months. The day on which participants are required to complete the EPDS will be selected at random from each calendar month, and with no less than 2 weeks in between 2 consecutive sampling periods. On that day, we will select a random time between 10.00 and 22.00 to administer the EPDS. At that time, a notification will be displayed on a participant's phone asking her to complete the EPDS. They will then be able to accept the request or reject it. Outside the sampling period, participants will be allowed to complete as many assessments as they wish to. However, during the sampling period, participants will not be allowed to complete any additional assessments.

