### 3.5.2.2.2. Retrospective plus momentary assessment

Participants in this condition will be required to complete a sampling period of 4 consecutive days once a month for 6 months; this period will be randomly selected from each calendar month, with no less than 2 weeks in between 2 consecutive sampling periods. The sampling period will start on day 1 with an administration of the EPDS and will conclude with another administration of the EPDS on day 4. In between (i.e., days 1 to 4 of the sampling period) participants will be asked to complete EMA assessments on mood, sleep, energy, enjoyment and worry plus 2 contextual information questions 3 times a day. The sampling hours will run between 10.00 and 22.00. This 12-hour window will be divided into 3 periods of 4 hours each, and with no less than one hour in between 2 consecutive assessments. Participants will receive a notification prompting them to complete the assessment at random times within each 4-hour period. Participants will have the option to accept or reject the request in the notification. Outside the sampling period, participants will be allowed to complete as many assessments as they wish to. During the sampling period however, participants will not be allowed to complete any additional assessments.

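### The BYOD drop-out rule counts two consecutive missed assessments without defining the unit, in arms with 6 and up to 84 scheduled assessments, so the comparison between arms depends on how the rule is read

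*Combined protocol and SAP*

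**What the plan says.** Section 3.3.1.2.2 defines drop-out in the BYOD study twice. Its first sentence counts participants who "stop completing the retrospective or the retrospective plus momentary assessments before the end of the study". Its second says that "we will consider they have dropped out if they miss 2 consecutive assessments", and this event also triggers a phone notification asking for the reason.

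The schedules are:

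- Retrospective arm (3.5.2.2.1): "Participants in this condition will be asked to complete the EPDS once a month for 6 months", with sampling periods at least two weeks apart.
- Retrospective plus momentary arm (3.5.2.2.2): a four-day sampling period in each of six months, with an EPDS on day 1, an EPDS on day 4, and EMA three times a day on all four days. EMA prompts are spaced "with no less than one hour in between 2 consecutive assessments"; the monthly blocks are spaced "with no less than 2 weeks in between 2 consecutive sampling periods".

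Section 3.3.1.2.4 adds: "Each pre-specified assessment will be preceded by a prompt".

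The first secondary objective in 2.2.2 is "To assess differences in drop-out rates between the participants allocated to the retrospective assessment strategy" and those allocated to the other strategy. Section 3.8.2.8 compares the proportions between groups; it neither restates the unit nor names a test.

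**The concern.** One rule is applied to two very different schedules, and nothing says what one assessment is for this purpose. Three readings are open.

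1. **Per prompt.** Section 3.3.1.2.4 gives each pre-specified assessment its own prompt, and 3.5.2.2.2 speaks of consecutive assessments when it means EMA prompts and of sampling periods when it means months. This is the reading that the nearest wording favours.
2. **EPDS administrations only.** This gives 6 in one arm and 12 in the other.
3. **Monthly sampling period.** This is plausible because it fits the idea of stopping in the first sentence of 3.3.1.2.2, but no section defines a month as one assessment. Nothing says when a period of 14 items counts as missed.

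On the per-prompt reading, two misses on one day make a drop-out in the momentary arm, while the retrospective arm needs two missed months. A woman who misses two prompts and then resumes is also counted, although she has not stopped.

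At stake is the interpretation of a randomised comparison. The Background section names overburdening respondents as the risk of EMA. A difference produced by the counting rule would look like that effect.

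**Working it through.** **The plan's own figure.** The documents give no figure for the drop-out rule. The BYOD sample size (3.6) is 96 per arm: 1.96² × 0.25 / 0.10² = 96.04, which reproduces. It is based on adherence and is used below only for scale.

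**Scheduled assessments.**

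- Retrospective arm: 6 × 1 = 6.
- Momentary arm: 6 × (2 EPDS + 4 days × 3 EMA) = 6 × 14 = 84, of which 12 are EPDS and 72 EMA.
- The 84 is an upper count, because 3.5.2.2.2 does not say whether the two EPDS have prompts of their own. Baseline and voluntary assessments are left out.

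**Assumptions, not from the documents.** The mean miss probability is 10% per assessment, the same in both arms and for EPDS and EMA. Each woman has her own miss probability q, drawn from a beta distribution with mean 0.10. The ICC describes how strongly misses cluster within women.

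**Formula.** The probability of at least one run of two misses in n assessments is

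P(n) = 1 − Σₖ C(n−k+1, k) E[qᵏ(1−q)ⁿ⁻ᵏ].

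Check for n = 6 with independent misses: 1 − (0.531441 + 0.354294 + 0.065610 + 0.002916) = 0.0457.

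**Results when nobody truly stops.**

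| Clustering | Retrospective, n = 6 | EPDS only, n = 12 | EMA prompts only, n = 72 | All prompts, n = 84 |
|---|---|---|---|---|
| ICC 0.9 | 10.4% | 10.9% | 12.1% | 12.2% |
| ICC 0.7 | 10.9% | 12.7% | 16.7% | 17.0% |
| ICC 0.5 | 10.9% | 14.3% | 22% | 23% |
| Independent | 4.6% | 9.7% | 48% | 53% |

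Allowing runs only within a month changes the independent 84-item figure little, from 53.5% to 51.5%. Other miss rates with independent misses, 6 v 84 items: 1.2% v 18.0% at 5% missed, and 16.4% v 94.5% at 20% missed.

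**Monthly reading at ICC 0.7** (simulated with 2,000,000 beta draws; run of two in six periods). The retrospective arm stays at 10.9%. The momentary arm depends on what makes a period missed:

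- all 14 items missed (probability q¹⁴): 3.6%
- neither EPDS completed (q²): 8.0%
- day-1 EPDS missed (q): 10.9%
- any item missed (1 − (1−q)¹⁴): about 21%

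Identical behaviour can therefore put the momentary arm below, level with or above the other arm.

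**Scale.** With 96 per arm and a two-sided 5% comparison of proportions, power is

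Φ{(|p₁−p₂|√96 − 1.96√(2p̄(1−p̄))) / √(p₁(1−p₁)+p₂(1−p₂))}.

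The chance of declaring the per-prompt artefact (84 items) significant is about 60% at ICC 0.5, 23% at ICC 0.7 and 6% at ICC 0.9. The plan names no test, so this only shows how visible the artefact would be.

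**Check of the remedy when nobody stops.** A closing run of two missed periods, judged on one EPDS per period, has probability E[q²] in both arms: 1.0% (independent), 5.5% (ICC 0.5), 7.3% (ICC 0.7) and 9.1% (ICC 0.9). If either EPDS of a period counted, the momentary arm would have E[q⁴]. At ICC 0.7, E[q²] = 0.1 × 1.042857/1.428571 = 0.0730 and E[q⁴] = 0.0730 × (2.042857/2.428571) × (3.042857/3.428571) = 0.0545, so 7.3% v 5.4%. A single common EPDS per period is therefore the better main criterion.

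**The case against.** The strongest reply is that this is one of many secondary objectives in a feasibility study. The sample size rests on adherence, 2.2.3 states no hypothesis on drop-out, and no test is named. That limits the weight of the point but does not remove it: the comparison between randomised arms is explicitly planned.

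A second reply is that misses cluster strongly within women, so the independent case overstates the problem. That stands. The 4.6% v 53% contrast is an extreme, and at ICC 0.9 the gap is under two percentage points.

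A third reply is that a monthly unit is obviously meant. A reader might infer this from 3.1, where the second arm is to "complete the EPDS, plus 4 days of EMA of mood, sleep, worry, enjoyment and energy, plus EPDS once a month for 6 months" and this is followed by the arm's name in parentheses. There the name labels the experimental condition; it does not make a month one assessment. The first sentence of 3.3.1.2.2 uses the plural for each arm's set of assessments. The monthly reading remains possible, but it would still need a rule for when a period is missed.

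Finally, not counting women who resume changes what the two-miss rule says. That is a design choice separate from the ambiguity, so the plan's rule should be kept as a sensitivity analysis.

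**Conclusion.** The point holds and should be fixed. The rule has no defined unit. On the reading that its wording favours, equal missing behaviour gives unequal drop-out: at a 10% mean miss rate the excess in the momentary arm is about 12 percentage points at ICC 0.5, 6 at ICC 0.7 and 2 at ICC 0.9. The EPDS-only reading gives a smaller excess, about 2 points at ICC 0.7 and 5 if misses are independent.

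These sizes rest on assumed miss rates and clustering that are equal in both arms. A reader might infer that the momentary arm will show drop-out near 50%, or that any observed difference must be an artefact. The documents support neither inference: they give no miss rates, and the artefact runs from decisive to negligible. The adherence-based sample size is not affected.

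**What to change.** Reword 3.3.1.2.2 and 3.8.2.8 before the data are seen.

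- **Unit.** For the between-arm comparison, use the monthly sampling period in both arms, judged on one scheduled EPDS per period: the monthly EPDS in the retrospective arm and the day-1 EPDS in the momentary arm. Voluntary EPDS outside the sampling period do not count as completing it.
- **Event.** A woman has dropped out if she formally withdraws before 6 months (allowed at any stage under 5.2), or if at least the last two periods through month 6 are missed, dated to the first period of that run.
- **Sensitivity analyses.** (a) Either the day-1 or the day-4 EPDS completes a period. (b) The plan's two-consecutive-misses rule applied to monthly periods, counting women who later resume.
- **Descriptive result.** In the momentary arm, report separately the women who stop EMA but continue the EPDS, and the reverse. The main definition does not show them.
- **Notification.** State the unit of its trigger separately.

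The downside is that a woman who silently stops only in month 6 is not a drop-out, although the first sentence of 3.3.1.2.2 could be read to include her. She still appears as non-adherent under 3.3.1.2.3. The cost is rewording, two sensitivity analyses and one descriptive result. No new data are needed, because scheduled and completed assessments are already required for adherence and timeliness.

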#### *3.8.2.8. Drop-out rates*

We will compare the proportion of potential participants who drop-out the study before 6 months (out of the total number of participants enrolled in the study) between the experimental groups.

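### Section 3.3.1.2.2 gives two drop-out definitions that can disagree, with no rule for a woman who misses two assessments and then resumes

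*Combined protocol and SAP*

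**What the plan says.** Section 3.3.1.2.2 of the combined protocol and SAP defines the drop-out rate as the proportion of participants "who stop completing the retrospective or the retrospective plus momentary assessments before the end of the study", which it equates with 6 months. For the app study it then gives an operating rule: "we will consider they have dropped out if they miss 2 consecutive assessments". The only stated consequence of meeting that rule is that "a notification on their phones will ask them to complete a question about the reason for not completing the assessments". The section does not say that prompts or access end, or what happens to the classification if the woman resumes.

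Section 3.8.2.8 carries drop-out into the analysis: "We will compare the proportion of potential participants who drop-out the study before 6 months". It does not cite the two-miss rule.

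The retrospective schedule in section 3.5.2.2.1 is monthly: "Participants in this condition will be asked to complete the EPDS once a month for 6 months". Each request arrives at a random time on a random day, and of the participants it says: "They will then be able to accept the request or reject it". In the other arm, section 3.5.2.2.2 sets a four-day period each month with an EPDS on day 1 and on day 4 and EMA three times a day. The drop-out rule does not say which of these counts as an assessment.

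**The concern.** Stopping and missing two in a row are different events. Because nothing removes a woman from the app after two misses, she can meet the second definition and still take part to the end. An analyst applying the operating rule counts her as a drop-out; an analyst applying the first sentence does not. Both can claim to follow the plan.

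Drop-out is the first secondary objective in section 2.2.2 of a study whose primary objective is feasibility, and section 6.5 says the findings will inform a later trial. Under the operating rule, the reported rate mixes women who abandoned the app with women who skipped two months and returned. Full adherence already has its own endpoint (section 3.3.1.2.3), so drop-out adds information only if it captures abandonment. Leaving the choice open until the data are seen would also make the between-arm comparison depend on the analyst.

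**Working it through.** **The plan's own figure.** The documents give no drop-out rate. The app-study sample size in section 3.6 reproduces as a precision calculation: 1.96² × 0.5 × 0.5 / 0.10² = 96.04, so 96 per arm (the proportion 0.5 is assumed). It rests on adherence, so this point does not change it.

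**Patterns in the retrospective arm.** Six monthly EPDS give 2⁶ = 64 complete/miss patterns. Those with no two adjacent misses number 1 + 6 + 10 + 4 = 21 (for 0, 1, 2 and 3 misses), so 64 − 21 = 43 are flagged. They divide as follows:

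- 19 include a completed month 6
- 16 miss both months 5 and 6
- 8 have an earlier run of misses, complete month 5 and miss month 6

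The 19 satisfy the two-miss rule although the woman was still completing assessments at the end. This disagreement needs no assumption about miss rates.

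**Illustration of size.** Assume each prompt is missed independently with probability m, nobody leaves, and q = 1 − m.

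- P(flagged) = 1 − (q⁶ + 6mq⁵ + 10m²q⁴ + 4m³q³). At m = 0.10: 1 − (0.53144 + 0.35429 + 0.06561 + 0.00292) = 0.0457.
- P(flagged and month 6 completed) = q × [1 − (q⁵ + 5mq⁴ + 6m²q³ + m³q²)]. At m = 0.10: 0.9 × (1 − 0.96309) = 0.0332, and 0.0332 / 0.0457 = 73%.
- Under the rule proposed below, a label requires months 5 and 6 both missed: m².

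| m | Flagged by two-miss rule | Of these, completed month 6 | Labelled under the proposed rule |
|---|---|---|---|
| 10% | 4.6% | 73% | 1% |
| 20% | 16.4% | 66% | 4% |
| 30% | 32.7% | 59% | 9% |

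With 96 women and m = 20%, that is about 96 × 0.164 = 16 labelled, of whom 96 × 0.108 = 10 completed month 6, against 96 × 0.04 = 4 under the proposed rule.

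**Why the unit matters.** The momentary arm has 2 × 6 = 12 EPDS and 3 × 4 × 6 = 72 EMA prompts, 84 in all. The probability of no run of two misses in n assessments follows a(n) = q·a(n−1) + mq·a(n−2), with a(0) = a(1) = 1. At m = 10, 20 and 30%, the two-miss rule flags 9.7, 32.2 and 57.4% if only the 12 EPDS count, and 53.5, 94.5 and 99.8% if all 84 count. The retrospective arm has 4.6, 16.4 and 32.7% with identical behaviour per prompt.

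**The case against.** A two-consecutive-miss rule is a reasonable operational definition: it forgives an isolated miss, and in the retrospective arm it means two successive months without a response. Section 3.5.2.2.1 does not say that a prompt expires, and timeliness (section 3.3.1.2.4) is a separate endpoint from adherence, so late completion may be possible and misses rarer than the illustration supposes. The documents supply no miss rate. Assuming that nobody leaves makes every label false by construction, so the percentages show what can happen, not the expected bias. Drop-out is a secondary objective. All of this stands. None of it tells the analyst how to classify a woman who resumes.

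Some stronger readings are tempting and not supported:

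- A reader might infer that the drop-out status is permanent. The plan says nothing on reversal; the gap is the absence of a rule.
- A reader might take the rule to cover any two misses. It requires two in succession: 57 patterns have two or more misses, and 14 of these are not flagged.
- A reader might conclude that stopping at month 6 always escapes. It does in the retrospective arm, where it is one miss. In the momentary arm, skipping the whole month-6 period is 14 consecutive misses (2 EPDS and 12 EMA) and is flagged.
- A reader might prefer to count anyone with no EPDS from some month through month 6. A single missed final EPDS would then be drop-out. With nobody leaving, this labels a share m of the retrospective arm (10, 20, 30%) but, because the momentary arm has two EPDS in month 6, only m² there (1, 4, 9%). It would create a between-arm difference of its own and should not be adopted.

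**Conclusion.** The concern holds as a conflict between two stated definitions. Followed literally, the operating rule labels as drop-outs women who have not stopped, contrary to the first sentence of the same section, and section 3.8.2.8 does not settle which governs. The disagreement is certain from the text (19 of 43 flagged patterns in the retrospective arm). Its size in the trial is unknown: the 4.6, 16.4 and 32.7% figures rest on assumed miss rates, independent misses and no true departures. The undefined unit adds a second problem, since one rule applied to 6 assessments in one arm and up to 84 in the other lets schedule density drive the comparison. The sample size is unaffected.

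**What to change.** In sections 3.3.1.2.2 and 3.8.2.8, count a woman as dropped out only if she withdraws explicitly, or misses two consecutive monthly assessments and completes no later scheduled assessment through month 6. Date drop-out at her last completed assessment. Apply this by month in both arms with the same unit, for example the day-1 EPDS of each sampling period in the momentary arm and the monthly EPDS in the retrospective arm. Keep two consecutive misses as the trigger for the reason question, and report women who trigger it and then return as intermittent in a separate row.

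The cost is a few sentences. The adherence endpoint already requires knowing which scheduled assessments each woman completed, so no new data are needed. There are two downsides. Status is final only at 6 months. A woman who stops only at month 6 cannot be told from one with an isolated miss: in the illustration m(1 − m), or 9, 16 and 21%, complete month 5 and miss month 6. Month-6 completion should therefore be reported by arm beside the drop-out rate.
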